##### *2.4.4.4.2 Absolute change from baseline in FEV1 (% Predicted and L), FEV1/FVC, FCV (% Predicted and L),*

Descriptive statistics for values and changes from baseline in FEV1 (% Predicted and L), FEV1/FVC, FCV (% Predicted and L) will be presented by treatment arm and background therapy status for each time point.

#### **2.4.5 Analyses of safety data**

The summary of safety results will be presented by treatment arm on the basis of the safety population.

### ***General common rules***

All safety analyses will be performed on the safety population as defined in [Section 2.3.2](#), unless otherwise specified, using the following common rules:

- Safety data in patients who do not belong to the safety population (eg, exposed but not randomized) will be listed separately. The baseline value is defined in [Section 2.1.4](#).
- The potentially clinically significant abnormality (PCSA) values are defined as abnormal values considered medically important by the Sponsor according to predefined criteria/thresholds based on literature review and defined by the Sponsor for clinical laboratory tests, vital signs, and ECG (PCSA version dated March 2014 [[Appendix A](#)]).
- PCSA criteria will determine which patients had at least 1 PCSA during the TEAE period, taking into account all evaluations performed during the TEAE period, including unscheduled or repeated evaluations. The number of all such patients will be the numerator for the on-treatment PCSA percentage.
- The treatment-emergent PCSA denominator by arm for a given parameter will be based on the number of patients assessed for that given parameter in the TEAE period by treatment arm on the safety population.
- For quantitative safety parameters based on central laboratory/reading measurements, descriptive statistics will be used to summarize results and change from baseline values by time point and treatment arm. Summaries will include the endpoint baseline value, the last on-treatment value and change from baseline, the worst on-treatment value and change from baseline. The last on-treatment value is commonly defined as the last value collected during the treatment period (see [Section 2.1.4](#)). The worst on-treatment value is defined as the nadir and /or the peak post-baseline during the treatment period according to the direction (minimum or maximum) of the abnormality as defined in the PCSA list.
- All measurements (scheduled or unscheduled) will be re-allocated as given in [Section 2.5.4](#) and re-allocated visits measurements will be included in the by-time point summary.
- The analysis of the safety variables will be essentially descriptive and no systematic testing is planned. Relative risks versus placebo and their 95% CIs may be provided, if relevant.

#### **2.4.5.1 Analyses of adverse events**

##### ***Generalities***

The primary focus of AE reporting will be on TEAE as defined in [Section 2.3.2](#). Pre-treatment and post-treatment adverse events will be described separately.

If an AE date/time of onset (occurrence, worsening, or becoming serious) is incomplete, an imputation algorithm will be used to classify the AE as pre-treatment, treatment-emergent, or post-treatment. The algorithm for imputing date/time of onset will be conservative and will classify an AE as treatment emergent unless there is definitive information to determine it is pre-

treatment or post-treatment. Details on classification of AEs with missing or partial onset dates are provided in [Section 2.1.4.1](#).

Adverse event incidence tables will present by SOC, HLGT, HLT, and PT, for each treatment arm, the number (n) and percentage (%) of patients experiencing an AE sorting based on results of column all. Multiple occurrences of the same event in the same patient will be counted only once in the tables within a treatment period. The denominator for computation of percentages is the safety population within each treatment arm.

Sorting within tables ensures the same presentation for the set of all AEs within the observation period (pre-treatment, treatment-emergent, and post-treatment). For that purpose, the table of all TEAEs presented by SOC and PT sorted by the internationally agreed SOC order and decreasing frequency of PTs within SOCs will define the presentation order for all other tables unless otherwise specified. Sorting will be based on results of column all.

### *Analysis of all treatment-emergent adverse events*

The following TEAE summaries will be generated for the safety population.

- Overview of TEAEs by treatment arm and by background therapy status, summarizing number (%) of patients with any
  - Treatment-emergent adverse event
  - Serious treatment-emergent adverse event
  - Treatment-emergent adverse event leading to death
  - Treatment-emergent adverse event leading to permanent treatment discontinuation
- All TEAEs by primary SOC, HLGT, HLT, and PT, showing number (%) of patients with at least 1 TEAE sorted by the SOC internationally agreed order. The other levels (HLGT, HLT, and PT) will be presented in alphabetical order. This table will be presented by treatment arm.
- All TEAEs by primary SOC and PT, showing the number (%) of patients with at least 1 TEAE, sorted by the internationally agreed SOC order and by decreasing incidence of PTs within each SOC. This sorting order will be applied to all other tables, unless otherwise specified. This table will be presented by treatment arm and by background therapy status.
- All TEAEs regardless of relationship and related by primary SOC, HLGT, HLT and PT, showing the number (%) of patients with at least 1 TEAE, sorted by the internationally agreed SOC order. The other levels (HLGT, HLT, and PT) will be presented in alphabetical order. This table will be presented by treatment arm and by background therapy status.
- All TEAEs by primary SOC and PT, showing the number (%) of patients with at least 1 TEAE, sorted by the internationally agreed SOC order and by decreasing incidence of PTs within each SOC. This table will be presented by treatment arm and by background therapy status.

- All TEAEs by maximal severity, presented by primary SOC and PT, showing the number (%) of patients with at least 1 TEAE by severity (ie, mild, moderate, or severe), sorted by the sorting order defined above. This table will be presented by treatment arm.

***Analysis of all treatment emergent serious adverse event(s)***

- All treatment-emergent serious adverse events by primary SOC, HLGT, HLT, and PT, showing the number (%) of patients with at least 1 serious TEAE, sorted by the internationally agreed SOC order. The other levels (HLGT, HLT, and PT) will be presented in alphabetical order. This table will be presented by treatment arm.
- All treatment-emergent serious adverse events by primary SOC and PT, showing the number (%) of patients with at least 1 serious TEAE, sorted by the internationally agreed SOC order and by decreasing incidence of PTs within each SOC. This table will be presented by treatment arm and by background therapy status.
- All treatment-emergent serious adverse events regardless of relationship and related to IMP, by primary SOC, HLGT, HLT, and PT, showing the number (%) of patients with at least 1 treatment-emergent serious adverse event, sorted by the internationally agreed SOC order. The other levels (HLGT, HLT, and PT) will be presented in alphabetical order. This table will be presented by treatment arm.
- All treatment-emergent serious adverse events regardless of relationship and related to IMP, by primary SOC and PT, showing the number (%) of patients with at least 1 serious TEAE, sorted by the internationally agreed SOC order and by decreasing incidence of PTs within each SOC. This table will be presented by treatment arm and by background therapy status.
- Listings will be provided for all SAEs by treatment arm during on-treatment period.

***Analysis of all treatment-emergent adverse event(s) leading to permanent treatment discontinuation***

- All TEAEs leading to treatment discontinuation, by primary SOC, HLGT, HLT, and PT, showing the number (%) of patients sorted by the internationally agreed SOC order (column “All”). The other levels (HLGT, HLT, and PT) will be presented in alphabetical order. Listings will be provided for all TEAEs leading to permanent treatment discontinuation by treatment arm and patient. This table will be presented by treatment arm.
- All TEAEs leading to treatment discontinuation, by primary SOC and PT, showing the number (%) of patients with at least 1 TEAE, sorted by the internationally agreed SOC order and by decreasing incidence of PTs within each SOC. This table will be presented by treatment arm and by background therapy status.

- Description of the highest intensity (and size) of each symptom (using pre-specified eCRF-terms: Erythema, Swelling, Itch, Pain, Tenderness; or using MedDRA coding if Other) from “Reaction at Injection Site” eCRF complementary form. Number will correspond to the count of patients with treatment emergent local injection site reaction and the corresponding symptom. More than one symptom may be reported for each injection site reaction. In case of several occurrences of a symptom, the maximal intensity is used
- Number of double-blind IMP injections received up to the first event (1, 2, 3, 4,  $\geq 5$  to  $<10$ ,  $\geq 10$  to  $<20$ ,  $\geq 20$ )

In addition, the following variables will be tabulated for the ALT increase TEAEs:

- Number (%) of patients with at least one ALT increase TEAE
- Number (%) of patients who met the following symptoms:

- Asthenia
- Nausea
- Fever
- Pruritus
- Jaundice
- Joint pain
- Abdominal pain
- Vomiting
- Skin eruption
- Purpura
- Hepatomegaly
- Splenomegaly
- Lymph nodes enlarged
- Ascites
- Asterixis
- Confusion

In addition, the following variables will be tabulated for the ALT increase – Trigger Factors TEAEs:

- Number (%) of patients with at least one ALT increase – Trigger factors TEAE
- Number (%) of patients with:
  - Any blood transfusion within the last 12 months
  - Exposure to potential hepatotoxic environmental or occupational agent within the last 12 months
    - Duration of exposure
  - Alcohol consumption within the last 7 days prior to increase
    - Number of standard drinks
  - Traveled in country at risk of viral hepatitis within the last 6 months
  - Used addictive drug within the last 12 months
    - Details of addictive drug
    - IV administration intake
    - Time to first administration (in weeks)

In addition, the following variables will be tabulated for the other event TEAEs:

- [REDACTED]
- Number (%) of patients with at least one tuberculosis event TEAE
- Number (%) of patients with at least one anaphylaxis event TEAE

#### ***Analysis of pre-treatment and post-treatment adverse events***

An overview presenting number of patients with any pre-/post-treatment adverse events, serious pre-/post-treatment adverse events, pre-/post-treatment adverse events leading to death, pretreatment adverse events leading to permanent treatment discontinuation will be displayed by treatment arm. If only few patients (<10% of randomized patients) are concerned, a global listing will be provided.

#### **2.4.5.2 Deaths**

The following summaries of deaths will be generated for the safety population by treatment arm.

- Number (%) of patients who died by study period (on-study, on TEAE period, post-study) and reasons for death summarized on the safety population by treatment received and by background therapy.
- Deaths in nonrandomized patients or randomized but not treated patients
- Treatment-emergent adverse events leading to death (death as an outcome on the AE case report form page as reported by the Investigator) by primary SOC, HLGT, HLT, and PT showing number (%) of patients sorted by internationally agreed SOC order, with HLGT, HLT, and PT presented in alphabetical order within each SOC. This table will be presented by treatment received and by background therapy.
- Treatment-emergent adverse events leading to death (death as an outcome on the AE case report form page as reported by the Investigator) by primary SOC and PT showing number (%) of patients with at least 1 TEAE leading to death, sorted by internationally agreed SOC order and by decreasing incidence of PTs within each SOC. This table will be presented by treatment received and by background therapy.
- All pre-treatment adverse events leading to death by primary SOC and PT, showing the number (%) of patients, sorted by the internationally agreed SOC order and decreasing incidence of PTs within each SOC
- All post-treatment adverse events leading to death by primary SOC and PT, showing the number (%) of patients, sorted by the internationally agreed SOC order and decreasing incidence of PTs within each SOC
- Listings of deaths will be provided. For deaths in non-randomized patients or randomized and not treated patients, a distinct listing will be provided.

### **2.4.5.3 Analyses of laboratory variables**

The summary statistics (including number, mean, median, standard deviation, minimum and maximum) of all laboratory variables (central laboratory values and changes from baseline) will be calculated for each time point or study assessment (baseline, each post-baseline time point, endpoint) by treatment arm. This section will be organized by biological function as specified in [Section 2.1.4.3](#) (except for pregnancy test).

For parameters glucose, monocytes, basophils, eosinophils and bicarbonate, the last on-treatment and worst on-treatment value will also be provided.

The pH parameter will be described by category:  $\leq 4.6$ ,  $>4.6$  and  $<8$ ,  $\geq 8$ .

A specific description of the following parameters will be provided at baseline by treatment arm and overall treatment groups:

- Tuberculosis information using MedDRA CMQ and the specific “Tuberculosis Assessment” eCRF page (signs and symptoms at screening (Yes, No), treated for tuberculosis in the past (Yes, No), receiving Active Anti-TB Therapy at screening (Yes, No)) and Quantiferon®-TB Gold test result (Positive, Negative, Indeterminate).
- Serology tests: hepatitis B surface antigen (Positive, Negative, Borderline), hepatitis B surface antibody (Positive, Negative, Borderline), hepatitis B core antibody (Positive, Negative, Borderline) and hepatitis C antibodies (Reactive, Unreactive, Borderline).
-  connective tissue disorders using MedDRA CMQs.

The incidence of PCSAs (list provided in [Appendix A](#)) at any time during the TEAE period will be summarized by biological function and treatment arm whatever the baseline level and according to the following baseline status categories:

- Normal/missing
- Abnormal according to PCSA criterion or criteria

For parameters for which no PCSA criteria are defined, similar table(s) using the normal range will be provided.

Listings will be provided with flags indicating the out of range values as well as PCSA values.

#### ***Drug-induced liver injury***

The liver function tests, namely AST, ALT, alkaline phosphatase, and total bilirubin, are used to assess possible drug-induced liver toxicity. The proportion of patients with PCSA values at any post-baseline visit by baseline status will be displayed by treatment arm for each parameter. The

proportion of patients with PCSA values at any post-baseline visit will also be displayed by duration of exposure for each treatment arm.

A graph of distribution of peak values of ALT versus peak values of total bilirubin will also be presented. Note that the ALT and total bilirubin values are presented on a logarithmic scale. The graph will be divided into 4 quadrants with a vertical line corresponding to 3 x ULN for ALT and a horizontal line corresponding to 2 x ULN for total bilirubin.

Summarize the normalization by parameter (to  $\leq 1$  x ULN or return to baseline) of elevated liver function tests by categories of elevation (1-<3 x, 3 x, 5 x, 10 x, 20 x ULN for ALT and AST, 1.5 x ULN for alkaline phosphatase, and 1.5 x and 2 x ULN for total bilirubin), with the following categories of normalization: never normalized, normalized after IMP discontinuation. Note that a patient will be counted only under the maximum elevation category: 1-3, 3-5, 5-10, 10-20, >20.

Summarize the incidence of liver-related AEs by treatment arm. The selection of preferred terms will be based on the drug related hepatic disorder SMQ.

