	
 • Tolerability at the investigational medicinal product (IMP) injection site: 
 - Erythema (diameter and graded severity) - Swelling/induration/edema (diameter and graded severity) - Pain assessment 
Immunogenicity
 
Testing for anti-drug antibodies (ADA)
 
Biomarker quantification
 
 • Blood biomarkers which may predict response to drug, disease progression and provide evidence of drug action will be collected including but not limited to inter-cellular adhesion molecule 1 (ICAM1), TARC, periostin and HE4 • Archived blood samples will be performed for future assay of protein and mRNA biomarkers related to the diagnosis, progression, or therapeutic responsiveness of IPF 
Pharmacokinetics
 
Population PK analysis of plasma SAR156597 concentrations to predict PK parameters at steady state (Cmax, tmax, AUC0-168 &/or AUC0-336) and time to reach steady state.

ASSESSMENT SCHEDULE
	
The study will comprise 10 on-site visits AND 9 phone calls:
 
 • Visits: 
 - V1 screening visit between D -28 and Day -1 - V2 baseline visit at D1 (first dosing) - during the treatment period*: 
 - visit every 2 weeks from V2 to V5 - every 6 weeks from V5 to V6 - every 12 weeks from V6 to V8 - every 16 weeks from V8 to V9 (Week 52; last dosing) - V10 follow-up visit at Week 64 - A time window of ± 2 days will be allowed for each visit • Phone calls: 
 - For safety considerations at Weeks 8, 16, 20, 28, 32, 40, 44, 48 during the treatment period and at Week 58 during the follow-up period. 
*IMP administration being every week.

STATISTICAL CONSIDERATIONS
	
Sample size determination:
 
Based on prior clinical trial experience in IPF patients, it is estimated that the standard deviation (SD) of the absolute change in % predicted FVC at 52 weeks is approximately 12%. For the primary efficacy parameter of absolute change in % predicted FVC, 92 patients per treatment group will yield 80% power to detect a 5 percentage point difference between the treatment groups and placebo. Additional patients will be randomized in each regimen to allow for dropouts; therefore, approximately 100 patients

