 - *Ask patients to come back to the site 1 week later to receive fourth IMP administration and be monitored for at least 1 hour after dosing]*
- Schedule an appointment for Visit 4

10.1.4 Visit 4: on treatment / Week 4

- Record all concomitant medication use
- Inquire about AEs/SAEs
- Review patient booklet to assess local tolerability at the injection site and treatment compliance *[For Czech Republic only, per local requirement: sentence deleted]*
- Record vital signs including blood pressure, heart rate and weight
- Perform a complete physical examination
- Obtain (fasting) blood samples for complete clinical laboratory determinations including hematology and biochemistry profile,
- Obtain urine for urinalysis (dipstick)

- For women of childbearing potential:
 - perform urine pregnancy test. The patients should be instructed to do the urine pregnancy test at home on a monthly basis during the intervals in between on-treatment study visits for the duration of the study. In case of a positive pregnancy test, the patient should be advised to contact immediately the Investigator
 - dispense urine pregnancy test kit for monthly urine pregnancy test (1 month supply)
- Perform 12-lead ECG
- Perform blood sample for serum SAR156597 and for anti-SAR156597 antibodies (ADA)
- Perform blood sample for ANCA
- Perform blood sample for complement (C3, C4 and CH50)
- Call IVRS to register visit and obtain next treatments number
- Dispense and administer IMP
 - [For Czech Republic only, per local requirement:*
 - *Dispense and administer IMP*
 - *Patients will be monitored for at least 1 hour after dosing*
 - *Ask patients to come back to the site 1 week later to receive sixth IMP administration and be monitored for at least 1 hour after dosing]*
- Schedule an appointment for Visit 5

10.1.5 Visit 5: on treatment / Week 6

- Record all concomitant medication use
- Inquire about AEs/SAEs
- Review patient booklet to assess local tolerability at the injection site and treatment compliance *[For Czech Republic only, per local requirement: sentence deleted]*
- Record vital signs including blood pressure, heart rate and weight
- Perform a complete physical examination
- Call IVRS to register visit and obtain next treatments number
- Dispense and administer IMP
 - [For Czech Republic only, per local requirement:*
 - *Dispense and administer IMP*
 - *Patients will be monitored for at least 1 hour after dosing*

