 - *For administration at patient's home, arrangements must be made for qualified site personnel and/or professional caregiver to administer IMPs at 1-week interval*
 - *Provide the patient with a booklet to record information pertaining to the injections to be performed at home as well as the treatment kit]*

- Schedule an appointment for phone call at week 8

10.1.6 Phone call: on treatment / Week 8, Week 16, Week 20, Week 28, Week 32, Week 40, Week 44, and Week 48

- Record all concomitant medication use
- Inquire about AEs/SAEs.
- Ask about the result of urine pregnancy test
- Assess local tolerability at the injection site

10.1.7 Visit 6, Visit 7 and Visit 8: on treatment / Week 12, Week 24, and Week 36

- Record all concomitant medication use
- Inquire about AEs/SAEs
- Review patient booklet to assess local tolerability at the injection site and treatment compliance
- Record vital signs including blood pressure, heart rate and weight
- Perform a complete physical examination
- Obtain (fasting) blood samples for complete clinical laboratory determinations including hematology and biochemistry profile
- Obtain urine for urinalysis (dipstick)
- For women of childbearing potential:
 - perform urine pregnancy test. The patients should be instructed to do the urine pregnancy test at home on a monthly basis during the intervals in between on-treatment study visits for the duration of the study. In case of a positive pregnancy test, the patient should be advised to contact immediately the Investigator
 - dispense urine pregnancy test kits for monthly urine pregnancy tests (sufficient monthly supplies to last until the next scheduled on-site visit.
- Perform 12-lead ECG
- Perform blood sample for serum SAR156597 and for anti-SAR156597 antibodies (ADA)
- Perform blood sample for ANCA
- Perform blood sample for complement (C3, C4 and CH50)

- **At Visit 7:** Obtain blood samples for biomarkers assessment and for archiving (potential future protein and mRNA biomarkers of interest)
- Obtain blood samples for archiving [REDACTED]
- Perform Pulmonary function tests: DLCO and FVC
- Perform a 6-MWT
- Perform Pulse oximetry
- Ask the patient to complete St George Respiratory Questionnaire
- **At Visit 8:** ask the patient to complete the EuroQol Questionnaire (EQ-5D-5L)
- Call IVRS to register visit and obtain next treatments number
- Dispense and administer IMP
- Schedule an appointment for next Visit

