10.2 DEFINITION OF SOURCE DATA

All evaluations that are reported in the e-CRF and in the patient booklet must be supported by appropriately identified source documentation.

10.3 HANDLING OF PATIENT TEMPORARY OR PERMANENT TREATMENT DISCONTINUATION AND OF PATIENT STUDY DISCONTINUATION

The IMP should be continued whenever possible. In case the IMP is stopped, it should be determined whether the stop can be made temporarily; permanent IMP discontinuation should be a last resort. Any IMP discontinuation should be fully documented in the e-CRF. In any case, the patient should remain in the study as long as possible.

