10.3.3 List of criteria for permanent treatment discontinuation

The patients may withdraw from treatment with the IMP if they decide to do so, at any time and irrespective of the reason, or this may be the Investigator's decision. All efforts should be made to document the reasons for treatment discontinuation and this should be documented in the e-CRF.

IMP will be permanently discontinued in case of the following events (refer to [Section 10.6](#) for details). The list is not intended to be exhaustive:

- [REDACTED]
- Symptoms of severe hypersensitivity or anaphylactic reactions (see [APPENDIX D](#) for definition)
- Severe skin reactions local to the site of IMP injection (see [APPENDIX E](#))
- Pregnancy
- Any adverse events, per Investigator's judgment, that may jeopardize the patient's safety

- Any laboratory abnormalities according to [APPENDIX F](#)
- All efforts should be made to reassess in a clinically relevant timeframe (using either local or central lab) the clinical significance of lab abnormalities and corrective actions before making a decision of permanent discontinuation of the IMP for the concerned patient.
- Any code breaking requested by the Investigator will lead to permanent treatment discontinuation
- At the specific request of the Sponsor

Any abnormal ECG parameter will be immediately rechecked for confirmation before making a decision of permanent discontinuation of the IMP for the concerned patient.

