The summary statistics (including number, mean, median, standard deviation, minimum and maximum) of all vital signs variables will be calculated for each visit or study assessment (baseline, each post-baseline time point, endpoint) by treatment group.

The incidence of PCSA at any time will be summarized by treatment group for each vital signs variable. Shift tables showing changes with respect to the baseline status will be provided. Listings will be provided with flags indicating the out of range values as well as the PCSA values.

Assessment of potential drug-induced liver injury

The liver function tests, namely ALT, AST, alkaline phosphatase and total bilirubin, are used to assess possible drug induced liver toxicity. The proportion of patients with PCSA values at any post-baseline visit by baseline status will be displayed by treatment group for each parameter. The proportion of patients with PCSA values at any post-baseline visit will also be displayed by duration of exposure for each treatment group.

A graph of distribution of peak values of ALT versus peak values of total bilirubin will also be presented. Note that the ALT and Total bilirubin values are presented on a logarithmic scale. The graph will be divided into 4 quadrants with a vertical line corresponding to 3xULN for ALT and a horizontal line corresponding to 2xULN for total bilirubin.

Summarize the normalization by parameter (to ≤ 1 ULN or return to baseline) of elevated liver function tests by categories of elevation (1-<3x, 3x, 5x, 10x, 20x ULN for ALT and AST, 1.5x ULN for Alkaline phosphatase, and 1.5x and 2x ULN for total bilirubin), with following categories of normalization: never normalized, normalized after IMP discontinuation. Note that a patient will be counted only under the maximum elevation category. 1-3, 3-5, 5-10, 10-20, >20

Summarize the incidence of liver related AEs by treatment group. The selection of PTs will be based on standardized MedDRA query (SMQ) for drug related hepatic disorders.

Analysis of the electrocardiogram data

The summary statistics (including number, mean, median, standard deviation, minimum and maximum) of all ECG variables will be calculated for each visit or study assessment (baseline, each post baseline time point, endpoint) by treatment group.

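### The liver-test normalization table has no category for a patient whose test normalizes while study drug continues, so recovery on drug cannot be read from it

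*SAP*

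**What the plan says.** SAP 2.4.5.3, under Drug-induced liver injury, plans a summary of liver-test normalization, meaning a return to the upper limit of normal (ULN) or below, or to baseline. It is set out by elevation class, starting at 1 to below 3 x ULN for ALT and AST, "with the following categories of normalization: never normalized, normalized after IMP discontinuation". Protocol 11.4.3 says the same: "with following categories of normalization: never normalized, normalized after IMP discontinuation". The SAP adds: "Note that a patient will be counted only under the maximum elevation category". Neither document gives a third outcome, a counting rule for recovery on drug, or the denominator.

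On dosing, Protocol 10.3 sets the default: "The IMP should be continued whenever possible". Protocol 10.3.1 allows temporary interruption and treats one longer than 30 days as permanent. Protocol 10.3.3 includes "Any laboratory abnormalities according to" Appendix F among the grounds for permanent discontinuation. The ALT flow chart in that appendix is not shown in the available text.

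**The concern.** A table of this kind is meant to show whether an elevation resolves on continued drug, resolves only after the drug is stopped, or does not resolve. With the two listed outcomes the first of these has no place. A patient with ALT at 2 x ULN at Week 4, normal at Week 12 and dosed to Week 52 can be handled in only three ways:

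- left out of the outcome rows;
- counted as never normalized, which overstates persistence;
- counted as normalized after discontinuation, which reads as recovery on withdrawal.

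The second and third are false, and the first hides the case. Each patient is counted once, under the maximum elevation, so no other row picks the case up. The choice would be made at programming, without a prespecified rule. ALT increase is an adverse event of special interest (AESI) here, and this is the only planned table of liver-test reversibility.

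**Working it through.** No stated figure depends on this table, so there is none to reproduce. The check asks whether the listed outcomes cover what the schedule can produce.

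**Inputs**

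- Post-baseline biochemistry: Weeks 4, 12, 24, 36, 52 and 64 (Protocol 1.2, flow chart). The Week 4 visit in Protocol 10.1.4 lists "Obtain (fasting) blood samples for complete clinical laboratory determinations including hematology and biochemistry profile", and the same item appears under "10.1.7 Visit 6, Visit 7 and Visit 8: on treatment / Week 12, Week 24, and Week 36".
- Last dose: Week 52. The Protocol synopsis gives the final on-treatment interval as "every 16 weeks from V8 to V9 (Week 52; last dosing".
- Samples are taken before that day's dose (Protocol 9.2.3). The Week 52 sample is therefore still an on-IMP sample, and only Week 64 is off IMP.

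**Enumeration for a patient dosed without interruption to Week 52**

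Take every pair (visit with elevated value, later visit with first normal value).

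- All pairs from six visits: 6 x 5 / 2 = 15.
- Pairs whose normal value falls on IMP (both visits among the first five): 5 x 4 / 2 = 10. These are 4→12, 4→24, 4→36, 4→52, 12→24, 12→36, 12→52, 24→36, 24→52 and 36→52.
- Pairs whose first normal value is at Week 64: 15 − 10 = 5.

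The 10 on-IMP pairs fit neither listed outcome. The other 5 fit the after-discontinuation outcome, reading discontinuation to include completion. The 10 of 15 counts patterns and does not estimate how many patients follow them.

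**Example records against the current list**

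| Record | Current list |
|---|---|
| ALT 2 x ULN at Week 4, normal at Week 12, IMP to Week 52 | No valid outcome |
| ALT 4 x ULN at Week 24, IMP stopped permanently, normal at next test | After discontinuation: correct |
| ALT 2 x ULN at Week 52, normal at Week 64 | After discontinuation: correct if completion is included |
| Elevated, IMP interrupted temporarily, normal during the gap, IMP resumed | Not defined |

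**Do other outputs supply the missing information in tabular form?**

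- The rates of potentially clinically significant abnormalities (PCSA), the peak ALT versus peak bilirubin graph and the liver-related AE incidence (SAP 2.4.5.3) do not use the normalization outcomes and do not report resolution.
- ALT and AST PCSA classes start above 3 x ULN (SAP Appendix A). The ALT AESI starts at 3 x ULN when baseline is below ULN (SAP 2.1.4.1). An ALT rise to 2 x ULN from a normal baseline reaches neither.
- The AESI listing (SAP 2.4.5.1) gives onset and recovery dates per patient, so ALT events that qualify can be traced by hand. Laboratory listings flag all out-of-range values. Neither tabulates recovery by dosing status.

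**The case against.** A reader might infer that the liver signal as a whole will be misreported, or that the evidence of recovery on drug is lost. The documents do not support either. Detection and size of a signal rest on the PCSA rates, the ALT-bilirubin graph and the AE and AESI tables, none of which uses these outcomes. The AESI listing with recovery dates and the flagged laboratory listings keep the patient-level facts. The safety analysis is also essentially descriptive, with no systematic testing (SAP 2.4.5).

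It can also be said that the SAP does not require the two outcomes to add up to all elevated patients. If the number elevated per class were shown, on-drug recovery could be read as the remainder. That would soften the problem, but the SAP does not state the denominator, and a remainder would still mix recovery on continued drug with recovery during an interruption.

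Finally, no size is shown. Neither document gives an expected rate of liver-test elevation, and without the ALT flow chart one cannot say how often larger elevations would be followed on continued IMP. That stands. The gap probably matters most in the 1 to below 3 x ULN class, but this is an assumption.

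**Conclusion.** The normalization table, in both SAP and protocol, is not exhaustive. A patient whose ALT, AST, alkaline phosphatase or bilirubin normalizes on continued IMP can only be omitted or mislabelled, and reversibility on drug cannot be read from the one table planned to show reversibility. The case is foreseeable from the sampling schedule and the policy of continuing IMP.

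This is a minor reporting defect, confined to one descriptive table. It has no effect on efficacy, type I error, sample size or any test. The conclusion rests on the listed outcomes being used as written and on scheduled predose sampling. The number of patients affected is unknown.

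**What to change.** In SAP 2.4.5.3, replace the two outcomes with four that are mutually exclusive and exhaustive, and show the number of patients elevated in each class as denominator:

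1. never normalized;
2. normalized while IMP was continued without interruption;
3. normalized during a temporary IMP interruption;
4. normalized after permanent IMP discontinuation or completion.

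Assign the category from the dosing record at the date of the first normal value. A cut-off at last IMP + 7 days (the SAP's treatment period) is not enough on its own. A value that normalizes during an interruption, with IMP then resumed, precedes the last dose and would be labelled as recovery on continued drug.

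The cost is a short change to the SAP text, two extra table rows and a derivation from dosing and laboratory dates already collected. The protocol wording can be superseded by an entry in the SAP's list of changes to the protocol's statistical section (SAP 1.5).
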